5.1.1 Other immunosuppressive and topical therapies for GVHD

Investigators are strongly encouraged but not mandated to continue other immunosuppressive therapies such as tacrolimus until at least a partial response is achieved; dose adjustment to achieve a desired drug level is allowed. However, subjects on prednisone may continue to taper prednisone at the discretion of the treating physician. Increase in prednisone dose (or prednisone equivalent dose) to a dose lower than or up to the prednisone dose at enrollment is acceptable to control disease symptoms, however, an increase in the dose of prednisone higher than the dose at enrollment will be considered a new systemic treatment and thus, therapy failure (1).

Subjects who start a new systemic immunosuppressive agent to control chronic GVHD (1) are considered therapy failures for which ruxolitinib will be discontinued. A short course of an immunosuppressive agent (<2 weeks) for a clearly documented non-chronic GVHD indication (e.g., stress dose steroids in someone on chronic steroids, a short pulse of steroids for an allergic reaction) will not be considered treatment failure unless it extends longer than 2 weeks. Topical therapies (including FAM or intra-oral narrow-band UVB phototherapy) can be initiated or stopped at the discretion of the treating physician while ruxolitinib is continued and are not considered treatment failures. For the purpose of this study, “FAM” (fluticasone, azithromycin and montelukast) therapy for lung GVHD will be considered a topical therapy.

5.2 Ruxolitinib dose modifications for toxicities

Ruxolitinib doses may be reduced in the event of toxicities. **The lowest permissive dose of ruxolitinib is 5 mg daily.**

Subjects with sclerotic GVHD have limited therapy options and may be willing to accept certain degree of toxicities. As such, this trial will allow treating physicians to use discretion regarding dose modifications of ruxolitinib but only under certain situations as specified in this section.

For subjects with grade 2 or lower hematologic or non-hematologic toxicities, ruxolitinib may be continued at the current dose or dose reduced by 50% at the discretion of the treating physician. Dose reduction by 50% (i.e. reduction to 5 mg BID in subjects receiving 10 mg BID) or temporary drug cessation is allowed in subjects with certain grade ≥ 3 hematologic or non-hematologic toxicities (see table below). Subjects who require drug cessation will resume ruxolitinib at a dose no higher than 5 mg BID for at least 2 weeks before resuming their previous dose. Subjects with grade 3-4 toxicities are required to undergo close monitoring with repeat testing of any abnormal laboratory or clinical parameter(s) within 2-7 days depending on specific circumstances.

Ruxolitinib dose modifications for toxicities

Toxicity (CTCAE Version 4.03) possibly, probably or definitely related to ruxolitinib	Dose modification	Subsequent starting dose
	Hematologic toxicities	
Grade 4 hematologic toxicities: (platelet count <25,000/ μ L, neutrophil count <500/ μ L, grade 4 febrile neutropenia with life-threatening consequences or requiring urgent interventions, life threatening anemia)	Temporary drug cessation until resolution to grade ≤ 2 or baseline ^a (mandatory)	5 mg BID for at least 2 weeks before considering dose escalation ^b
Grade 3 hematologic toxicities: (platelet count <50,000-25,000/ μ L, neutrophil count <1000-500/ μ L with or without fever [single episode of $>38.3^{\circ}\text{C}$ or $\geq 38^{\circ}\text{C}$ for more than 1 hour] without serious consequences)	Dose reduction by 50%, or temporary drug cessation until resolution to grade ≤ 2 or baseline ^a (at the discretion of investigator)	5 mg BID for at least 2 weeks before considering dose escalation ^b
Grade 2 or lower neutropenia or thrombocytopenia; and grade 3 or lower anemia (hemoglobin <8 g/dL)	Maintain dose or dose reduction by 50% (at the discretion of investigator)	If dose reduced, dose escalation at the discretion of the treating physician
Non-hematologic toxicities		
Grade 4 renal, hepatic or other non-hematologic toxicities (e.g. creatinine $>6.0 \times$ ULN, total bilirubin $>10.0 \times$ ULN, AST/ALT $>20.0 \times$ ULN, grade 4 hypertension ^c)	Temporary drug cessation until resolution to grade ≤ 2 or baseline ^a (mandatory)	5 mg BID for at least 2 weeks before considering dose escalation ^b
Grade 3 renal and hepatic toxicities (creatinine $>3.0 - 6.0 \times$ ULN, total bilirubin $>3.0 - 10.0 \times$ ULN, AST/ALT $>5.0 - 20.0 \times$ ULN)	Temporary drug cessation until resolution to grade ≤ 2 or baseline ^a (mandatory)	5 mg BID for at least 2 weeks before considering dose escalation ^b
Grade 4 increase in serum amylase or lipase ($>5.0 \times$ ULN)	Temporary drug cessation until resolution to grade ≤ 2 or baseline ^a (mandatory)	5 mg BID for at least 2 weeks before considering dose escalation ^b
Grade 3 or lower increase in serum amylase or lipase ($\leq 5.0 \times$ ULN)	Maintain dose or dose reduction by 50% (at the discretion of investigator)	If dose reduced, dose escalation at the discretion of the treating physician
Other grade 3 non-hematologic toxicities (e.g. grade 3 hypertension ^d)	Dose reduction by 50%, or temporary drug cessation until resolution to grade ≤ 2 or baseline ^a (at the discretion of investigator)	5 mg BID for at least 2 weeks before considering dose escalation ^b
Any grade 2 or lower non-hematologic toxicities	Maintain dose or dose reduction by 50% (at the discretion of investigator)	If dose reduced, dose escalation at the discretion of the treating physician
Criteria for permanent cessation of the study drug		
Subjects who cannot tolerate the lowest permissive ruxolitinib dose of 5 mg daily AND require cessation of drug for ≥ 4 weeks will be permanently removed from the study.		
Subjects who do not recover from grade 4 hematologic or non-hematologic toxicities possibly, probably or definitely related to ruxolitinib within 2 weeks of drug cessation will be permanently removed from the study. Recovery will be defined as resolution to grade ≤ 2 or baseline.		

^aRuxolitinib may be stopped without a taper in cases of unacceptable toxicities. If an abrupt cessation of ruxolitinib is required, investigators are strongly encouraged to consider starting or dose-escalating systemic glucocorticoid for at least a week (see Section 5.1 “Ruxolitinib taper prior to discontinuation”).

^bIf the drug is tolerated at a lower dose for at least two weeks, doses of ruxolitinib may be further increased to a maximum of 10 mg BID.

^cDefinition of grade 4 hypertension: Life-threatening consequences (e.g., malignant hypertension, transient or permanent neurologic deficit, hypertensive crisis); urgent intervention indicated.

^dDefinition of grade 3 hypertension: Stage 2 hypertension (systolic BP ≥ 160 mm Hg or diastolic BP ≥ 100 mm Hg); medical intervention indicated; more than one drug or more intensive therapy than previously used indicated.

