5.1 Treatment Schedule and Administration: Ruxolitinib

Drug	Dose/Frequency	Duration	Administration
Ruxolitinib	10 mg BID	6 months, may extend up to 12 months	Oral

Subjects will receive oral ruxolitinib at a dose of 10 mg twice daily. Doses may not exceed 10 mg twice daily. Subjects will record their intake on a medication diary provided to them. Ruxolitinib will be continued for 6 months, unless there is intolerable toxicity, chronic GVHD progression requiring additional systemic treatment or relapse of the underlying malignancy. Subjects with mixed responses or chronic GVHD progression prior to 6 months of therapy that does not require initiation of additional agent are allowed to continue ruxolitinib for the complete 6 month duration. Therapy duration of 6 months will ensure adequate exposure to ruxolitinib, and is important because of the limited options for therapy in the study population and limitations of the current response assessment.

Extended treatment

Subjects who continue to have stable disease, mixed responses or partial/complete responses at the end of 6 months may continue the drug for a total of 12 months. Subjects with chronic GVHD progression (not including stable disease or mixed responses) at the end of 6 months will stop ruxolitinib, regardless of whether or not a new systemic therapy has been added.

Ruxolitinib taper prior to discontinuation

At the end of 6 months, or 12 months for subjects treated on extension study, ruxolitinib will be tapered over a month before discontinuation, for example, a dose reduction by 5 mg every 1-2 weeks. Ruxolitinib may be stopped without a taper in cases of unacceptable toxicities. If an UNMC IRB # 333-18, Protocol Version 1.6 dated 25Jan2021

abrupt cessation of ruxolitinib is required, investigators are strongly encouraged to consider starting or dose-escalating systemic glucocorticoid (prednisone dose ≥ 0.5 mg/kg/day or equivalent dose) for at least a week to avoid rebound symptoms. While coming off ruxolitinib, subjects should be carefully monitored for worsening of GVHD symptoms or any other withdrawal symptoms.

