5.2.1 Dose reduction for Concomitant Medications

50% dose reduction should be considered when using medicinal products which are dual inhibitors of CYP2C9 and CYP3A4 enzymes (e.g. fluconazole). **Avoid the concomitant use of ruxolitinib with fluconazole doses greater than 200 mg daily.**

When administering ruxolitinib with strong CYP3A4 inhibitors, the total daily dose should be reduced by approximately 50%. Strong CYP3A4 inhibitors include boceprevir, clarithromycin, cobicistat, conivaptan, danoprevir/ritonavir, eltegravir/ritonavir, grapefruit juice, idelalisib, indinavir, itraconazole, ketoconazole, lopinavir/ritonavir, LCL161, mibefradil, nefazodone, nelfinavir, posaconazole, ritonavir, saquinavir, sequinavir/ritonavir, telaprevir, telithromycin, voriconazole, indinavir/ritonavir, tipranavir/ritonavir, and troleandomycin.

No dose adjustment is necessary when co-administering ruxolitinib with strong CYP3A4 inducers.

No dose adjustment is necessary when co-administering ruxolitinib with CYP3A4 substrates.

Ruxolitinib did not decrease the exposure of a fixed dose oral contraceptive metabolized via the CYP3A4 pathway, thus demonstrating lack of CYP3A4 induction potential.

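### In six rows of the section 5.2 toxicity table the restart dose is fixed at 5 mg BID, which for subjects already below 10 mg BID equals or doubles the dose at which the toxicity occurred

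*Combined protocol and SAP*

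**What the plan says.** Section 5.1 assigns one dose: "Subjects will receive oral ruxolitinib at a dose of 10 mg twice daily. Doses may not exceed 10 mg twice daily". Section 5.2 then sets a floor, "The lowest permissive dose of ruxolitinib is 5 mg daily", and explains the reduction step with a single worked case: "Dose reduction by 50% (i.e. reduction to 5 mg BID in subjects receiving 10 mg BID) or temporary drug cessation is allowed" for certain toxicities of grade 3 or above. After a stop, subjects "will resume ruxolitinib at a dose no higher than 5 mg BID for at least 2 weeks before resuming their previous dose".

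The table in section 5.2 has nine rows of toxicities judged at least possibly related to the drug. In six of them the last column, for the subsequent starting dose, reads "5 mg BID for at least 2 weeks before considering dose escalation":

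- hematologic grade 4
- hematologic grade 3
- non-hematologic grade 4
- renal and hepatic grade 3
- amylase or lipase grade 4
- other non-hematologic grade 3

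Four of these six make cessation mandatory. The other two (hematologic grade 3 and other non-hematologic grade 3) give the investigator a choice: "Dose reduction by 50%, or temporary drug cessation until resolution to grade" 2 or lower, or to baseline. The three remaining rows cover lower-grade events. They fix no dose and leave any re-escalation to the physician.

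Footnote b permits a later increase, up to 10 mg BID, once a reduced dose has been tolerated for two weeks. Section 5.2.1 says that with strong CYP3A4 inhibitors "the total daily dose should be reduced by approximately 50" percent, and that a similar reduction should be considered with dual CYP2C9/CYP3A4 inhibitors.

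**The concern.** The fixed entry in the last column appears to have been written with a subject at 10 mg BID in mind, but several provisions of the same protocol put subjects below that dose. For those subjects the entry is no longer a reduction. The text describes restart as an interim step before the earlier dose is resumed, and footnote b presumes that the interim dose is the lower one. Neither description holds if the restart dose equals or exceeds the dose at which the toxicity arose.

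Two things are at stake. The first is subject safety: the six rows cover grade 3 and 4 events attributed at least possibly to the drug, and section 8.1.10 describes cytopenias as dose dependent. The second is uniform conduct across sites: the same event could be followed by a lower, equal or higher dose, with each site able to cite the protocol.

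**Working it through.** **Inputs**

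- Full dose: 10 mg BID = 20 mg/day (section 5.1).
- Reduction step: 50% (section 5.2 text and table).
- Floor: 5 mg/day (section 5.2).
- Table restart entry in six rows: 5 mg BID = 10 mg/day (section 5.2 table).

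**Step 1: reproduce the protocol's own example.** 20 mg/day × 0.5 = 10 mg/day = 5 mg BID. This matches the text and the table entry, so the passages agree for a subject at 10 mg BID.

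**Step 2: confirm that lower doses are reachable.**

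- 5 mg BID arises from the interaction rule in 5.2.1 (20 × 0.5 = 10 mg/day), from a discretionary 50% reduction for toxicity of grade 2 or lower, or from an earlier restart.
- 5 mg daily arises from a further 50% reduction (10 × 0.5 = 5 mg/day). It is the stated floor, and the criterion for permanent cessation refers to subjects at that dose.

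**Step 3: compare the two columns at each dose.** Ratio = table entry (10 mg/day) ÷ daily dose when the toxicity occurred.

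| Dose at toxicity | mg/day | 50% of it | Table entry | Ratio to dose at toxicity | Ratio to 50% dose |
|---|---|---|---|---|---|
| 10 mg BID | 20 | 10 | 10 | 10/20 = 0.5 | 10/10 = 1.0 |
| 5 mg BID | 10 | 5 | 10 | 10/10 = 1.0 | 10/5 = 2.0 |
| 5 mg daily | 5 | 2.5 (below the floor) | 10 | 10/5 = 2.0 | 10/2.5 = 4.0 |

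The first ratio applies to all six rows. The last column matters only for the two rows that offer a 50% reduction.

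**Step 4: see whether another passage resolves it.**

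- The sentence limiting restart to no more than 5 mg BID sets a ceiling. A restart at 5 mg BID meets it whatever the earlier dose, so it does not rule out an unchanged or doubled dose. It covers only "Subjects who require drug cessation will resume ruxolitinib at a dose no higher than 5 mg BID for at least 2 weeks before resuming their" earlier dose, so it says nothing about a subject whose dose was reduced without a stop.
- Footnote b presumes a reduced dose but does not require one. It also allows a later rise to 10 mg BID without mentioning the interaction reduction in 5.2.1, a related gap.
- The discretion that section 5.2 gives physicians is confined to the situations it lists. In these six rows the last column states a dose, not a range.

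**Step 5: vary the reading of the last column.** If it applies only after cessation, the disagreement with the 50% option in the two mixed rows goes away. The ratios of 1.0 and 2.0 remain for subjects stopped at 5 mg BID and 5 mg daily.

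**The case against.** The strongest defence is that the table was drafted for the assigned dose. Every subject is assigned 10 mg BID, and for that dose the text, table and footnote b agree exactly. The column heading most naturally means the dose at which drug is started again after a stop; on that reading the four mandatory-cessation rows contain no clash between columns, and the two mixed rows lose theirs. The doubling case needs a subject already at the floor who then has a qualifying drug-related event, and it takes one cell literally against its own footnote. Other safeguards limit the risk: grade 3-4 toxicities are retested within 2 to 7 days, restart after a stop waits for resolution to grade 2 or lower or to baseline, subjects who do not recover from a grade 4 event within two weeks are removed, and escalation is optional.

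Much of this stands, and it rules out three stronger readings that a reader might infer:

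- That the table imposes one restart dose on everyone. It does not: three of the nine rows fix no dose.
- That the ceiling sentence contradicts the table. It does not: 5 mg BID satisfies a limit of 5 mg BID.
- That the restart column conflicts with the 50% reduction throughout. It can do so in two rows only, and only if the column also governs reductions without a stop.

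The defence does not close the gap. The protocol itself provides for subjects at 5 mg BID and 5 mg daily, and no passage says what the fixed entry becomes for them. The after-cessation reading is plausible but unstated, and it leaves the restart at 1.0 or 2.0 times the earlier dose. That the surrounding text presumes a lower restart shows that the cell does not fit; it does not give sites a rule to follow. The safeguards reduce the consequences without settling the dose.

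**Conclusion.** The inconsistency is real but narrow. In six of nine rows the stated restart dose is 0.5 times the dose at toxicity for subjects at 10 mg BID, as intended, but 1.0 times at 5 mg BID and 2.0 times at 5 mg daily. The last two do not fit the text's description of restart as a step before the previous dose, or footnote b. In two rows there is a further disagreement with the 50% option for a subject at 5 mg BID (10 mg/day against 5 mg/day), conditional on how the last column is read.

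The conclusion assumes that the table is followed as written and that some subjects are below 10 mg BID when a qualifying toxicity occurs. The documents do not say how many that would be. A reader might infer an effect on the trial's inference; none follows, because alpha, power and sample size do not depend on this rule. The case for correcting it rests on subject safety and consistent conduct across sites.

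**What to change.** For subjects taking less than 10 mg BID when the toxicity occurs, the sponsor should reconcile five passages so that they lead to one result: the restart column, the 50% reduction column, the ceiling sentence in the section 5.2 text, footnote b and section 5.2.1. The table should also state whether its last column applies only after cessation or also after a reduction without a stop. The choice of dose or rule is the sponsor's, and none is proposed here.

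The cost is a wording amendment to one table, its footnote and the related text. No change to the design, sample size or analysis is needed.

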5.4 Duration of Study and Follow-up

We estimate that there will be 47 subjects dosed over a 2.5-year period. After accrual is met, we plan to follow the subjects for up to 2 years; the follow-up duration is discussed in detail in the table below.

GVHD response evaluation every 3 months	Therapy duration	End of therapy safety evaluation (30-40 days after the last dose of the study drug)	Last follow-up for GVHD evaluation	Data collection
Stable disease or mixed responses at the end of 6 months	6 to 12 months followed by taper over 1 month ¹	8 months; If therapy continued till 12 months and tapered over the next month, 14 months ²	At the end of 6 months; If therapy continued until 12 months, up to 24 months from the study enrollment ³	Data on survival, relapse of malignancy, subsequent GVHD treatment will be collected till subjects are removed from the study, death or up to a total of 2 years. For subjects who have completed last follow-up for GVHD evaluation, further data may be collected via review of medical records or telephone interview.
Partial/complete responses at the end of 6 months	6 to 12 months followed by taper over 1 month ¹	8 months ⁴ ; If therapy continued till 12 months and tapered over the next month, 14 months ²	Up to 24 months from the study enrollment ³	
GVHD progression, toxicity or relapse ⁵	<6 months (may stop without a taper)	About 30 days after the last dose	At the end of 6 months	

¹If no intolerable toxicity, chronic GVHD requiring initiation of an additional systemic agent, or relapse of underlying malignancy within the 6 months of the study participation, ruxolitinib may be continued till 12 months

²If no toxicity concerns were raised at 12-month follow-up, this evaluation may be performed over the phone with a plan to see the subject in a follow-up at 15 months.

³The subject will be followed every 3 months until progression of chronic GVHD requiring initiation of an additional systemic agent, relapse of underlying malignancy or for a total of 2 years

⁴For subjects with partial or complete responses at 6 months, if no toxicity concerns were raised at 6-month follow-up, this evaluation may be performed over the phone with a plan to see the subject in a follow-up at 9 months.

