5.5.4 End of Month 6 Visit (+/-14 days)

Assessments at the end of month 6 visit will include:

- History and physical exam
- Clinical laboratory parameters (hematology and serum chemistry)
- Comprehensive GVHD assessment including digital pictures of range of motion (if abnormal) and any visible skin lesions, mapping of sclerotic areas (Appendix I)
- Patient reported outcomes
- Research blood collection for correlative studies
- Adverse event monitoring

Data on relapse of the underlying malignancy, survival, chronic GVHD flares, prednisone dose and use of other immunosuppressive agents will be captured at scheduled time points, and verified at each visit.

5.5.5 End of Month 9, 12, 15, 18, 21 and 24 Visit (+/-30 days) (Extended Treatment)

Subjects who maintain complete or partial response at the end of 6 months, OR receive extended therapy (see section 5.4 for details) will be followed every 3 months (+/-30 days) until start of another systemic treatment for chronic GVHD, relapse of underlying malignancy or for a total of 2 years to determine the duration of response.

Assessments at these visits will include:

- History and physical exam
- Clinical laboratory parameters (hematology and serum chemistry)
- Comprehensive GVHD assessment including digital pictures of range of motion (if abnormal) and any visible skin lesions, mapping of sclerotic areas (Appendix I)
- Patient reported outcomes
- Adverse event monitoring if receiving ruxolitinib within the past 30 days

Data on relapse of the underlying malignancy, survival, chronic GVHD flares, prednisone dose and use of other immunosuppressive agents will be captured at scheduled time points, and verified at each visit.

5.5.6 End-of-therapy or Safety Follow-up Visit (30-40 days after the last dose of ruxolitinib)

Subjects will undergo this visit 30-40 days after the last dose of ruxolitinib (see section 5.4 for details).

Assessments at safety follow-up visit will include:

- History and physical examinations
- Clinical laboratory parameters (hematology and serum chemistry)
- Comprehensive GVHD assessment (if a subject withdraws from study treatment prior to 3 or 6 month assessment time points)
- Adverse event monitoring

Subjects with grade 3-4 toxicities are required to undergo close monitoring with repeat testing of any abnormal laboratory or clinical parameter(s) within 2-7 days depending on specific circumstances.

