5.6 Criteria for Discontinuation of the Study Drug and Removal from Study

Subjects will discontinue the study drug for any of the following reasons:

- Progression of GVHD resulting in initiation of a new systemic immunosuppressive agent (also see Section 5.1.1)
- Development of an adverse reaction that necessitates discontinuation of the study drug, including any unresolved serious adverse event. Please see section 5.2 for further details.
- Development of a serious systemic allergic response or severe degree of intolerance to the study medication.
- Development of intercurrent medical problems that would make continued protocol therapy detrimental to the subject's safety.
- The subject chooses to discontinue treatment.

Subjects who stop study medication for GVHD progression or relapse of underlying malignancy will stop research visits except for the safety follow-up visit. Data may continue to be collected via chart review.

Subjects will be removed from the study (**study withdrawal**) for any of the following reasons:

- If at any time the requirements of this protocol are detrimental to the subject's wellbeing, the subject will be removed from the study. In this event, the reason(s) for withdrawal will be documented.
- The subject requests removal from the study.

The reason(s) for **study withdrawal** will be documented and no further information may be collected on the subject. The reason(s) for stopping study medication will be documented in the UNMC IRB # 333-18, Protocol Version 1.6 dated 25Jan2021

case report form. If available, the following information will be recorded in the case report form: GVHD status, date of relapse of underlying malignancy, date of death, cause of death, and autopsy report. Subjects who stop the study drug but do not withdraw from the study may remain in the study.

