Concomitant medications including systemic glucocorticoid ⁵	X				X	X ⁶	X ⁶

1. Testing for Hepatitis B, C and HIV completed prior to transplant will be acceptable. No additional testing is required for study eligibility.
2. If a subject withdraws from study treatment prior to the end of 3 or 6 month assessment time points, the comprehensive GVHD assessment should be completed at the End of Treatment/Safety follow up visit.
3. The correlative sample can be collected at any time during the scheduled visit.
4. Body mapping and digital pictures will be uploaded in the eCRF. The instructions are listed the CRF Completion Guidelines
5. For all subjects enrolled in this study including those enrolled in the past, data on only concomitant medications of interest (i.e. glucocorticoid, and other immunosuppressive agents including narrow band UVB phototherapy and extracorporeal photopheresis) should be collected at baseline, at each 3-monthly visit until the subject stops ruxolitinib and end of treatment/safety follow-up.
6. After the subjects stop ruxolitinib, if a new immunosuppressive agent is started for treatment of GVHD, only data on the new immunosuppressive medicine should be collected.
7. The subject should be called to check on dose compliance and lab results.
8. If the subject has stable disease, mixed responses or partial/complete response, the subject can continue to take ruxolitinib for a total of 12 months before tapering off the study drug. Please review section 5.1 for further details.

Section 8.0 Drug Formulation and Procurement

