8.1.11 Drug Accountability

Responsibility for drug accountability at the study site rests with the investigator; however, the investigator may assign some of the drug accountability duties to an appropriate pharmacist or designee. Inventory and accountability records must be maintained and readily available for inspection by the study monitor and are open to inspection at any time by any applicable regulatory authorities.

The investigator or designee will be expected to collect and retain all used, unused, and partially used containers of study medication until the end of the study. The Investigator or designee must maintain records that document:

- investigational product delivery to the study site
- the inventory at the site
- use by each subject including pill/unit counts from each supply dispensed
- product returned to the investigator or designee.

These records should include dates, quantities, batch/serial numbers (if available), and the unique code numbers (if available) assigned to the investigational product and study subjects.

The investigational product must be used only in accordance with the protocol. The investigator will also maintain records adequately documenting that the subjects were provided the study medication specified.

Completed accountability records will be archived by the site. If any unused ruxolitinib bottles remain at the end of the study, they will be accounted for by the site prior to study closure. If a site is able to destroy ruxolitinib at their premises, or through a certified vendor, they may do so upon authorization by the sponsor, provided their destruction policy is made available to the sponsor.

Section 9.0 Toxicity and Adverse Event Reporting Guidelines

This protocol will comply with monitoring and adverse event reporting requirements of the UNMC Fred & Pamela Buffett Cancer Center Data Monitoring plan. The protocol will adhere to the institutional and FDA guidelines for the toxicity reporting.

All subjects will be closely followed for toxicity from the time of informed consent until 30 days after last administration of study medication. The reporting is only for “study medication,” until 30 days after last administration of study medication.

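### Section 5.2 removes two drug-toxicity subgroups from the study where other sections only stop the drug, and 10.1 does not say how a toxicity stop without a month-6 assessment is counted

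*Combined protocol and SAP*

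**What the plan says.** Section 5.2 closes its dose-modification table with criteria for permanent cessation of the drug. One covers subjects who cannot tolerate 5 mg daily and "require cessation of drug for ≥ 4 weeks will be permanently removed from the study". The other covers subjects who do not recover from grade 4 toxicity possibly, probably or definitely "related to ruxolitinib within 2 weeks of drug cessation will be permanently removed from the study".

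Section 5.6 separates two outcomes. Adverse reactions stand in its list of reasons to discontinue the drug, with a pointer to 5.2. Removal from the study is a different list, labelled study withdrawal, with two reasons: the protocol's requirements harm the subject, or the subject asks to leave. After withdrawal, "no further information may be collected on the subject". By contrast, "Subjects who stop the study drug but do not withdraw from the study may remain in the study".

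In the 5.4 table, the row headed "GVHD progression, toxicity or relapse" covers therapy of under 6 months and sets the last GVHD evaluation at the end of 6 months. Footnote 5 confirms that intolerable toxicity belongs in that row. Section 5.5.6 adds to the safety visit a "Comprehensive GVHD assessment (if a subject withdraws from study treatment prior to 3 or 6 month assessment time points"), and note 2 to the Section 7.0 table says that in such cases "the comprehensive GVHD assessment should be completed at the End of Treatment/Safety follow up visit".

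Section 10.1 puts into the full analysis set subjects evaluable at 6 months and subjects who failed treatment earlier, including deaths. It excludes those who drop out before 6 months for reasons unrelated to treatment. Sections 1.3 and 10.2.1 define treatment failure as additional systemic therapy for chronic GVHD, relapse of malignancy, or death. The primary analysis uses this set.

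**The concern.** A site managing severe toxicity will turn to 5.2, and taken at its word 5.2 ends the subject's participation. That contradicts the month-6 evaluation in 5.4. If the site follows 5.2, the primary endpoint is not assessed for subjects whose drug toxicity was worst or most persistent, and a missed assessment cannot be recovered later.

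The analysis section does not close the gap. A subject who stops for drug toxicity and has no month-6 assessment is not evaluable at 6 months, is not a treatment failure unless one of the listed events occurs, and is not a dropout unrelated to treatment. No response status is assigned. In an open-label, single-arm trial, the analyst would then decide after seeing the data whether these subjects are in the denominator. Leaving out non-responders raises the reported response rate.

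**Working it through.** **1. The texts side by side, for a subject stopped early for related toxicity**

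| Source | Consequence |
|---|---|
| 5.2, heading | Drug stopped |
| 5.2, both sentences | Removed from the study |
| 5.6, drug-discontinuation list (points to 5.2) | Drug stopped; may remain in the study |
| 5.6, study-withdrawal list | Toxicity meeting 5.2 is not named |
| 5.4, row 3 and footnote 5 | GVHD evaluation at the end of 6 months |
| 10.1, inclusion | Not covered without a month-6 assessment or a failure event |
| 10.1, exclusion | Does not apply, because the reason is related to treatment |

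Only the two 5.2 sentences point to removal.

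**2. Can the safety visit stand in for month 6?** It takes place 30–40 days after the last dose. Taking month 6 as day 183 (an assumption), the ±14-day window is days 169–197. The visit can fall in it only if the last dose was between day 169 − 40 = 129 and day 197 − 30 = 167. Taking month 6 as day 180 to 184 moves the early limit to days 126–130. For earlier stops, the safety-visit assessment is not a month-6 assessment, and 10.1 does not say whether it may be used as one.

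**3. The plan's own design figures.** Section 10.1 continues if at least 5 of 18 respond and passes if at least 16 of 42 respond. The exact pass probability is the sum over x = 5 to 18 of P(X₁ = x) × P(X₂ ≥ 16 − x), with X₁ ~ Bin(18, p) and X₂ ~ Bin(24, p).
- p = 0.45: 0.841, matching the stated 84% power.
- p = 0.25: 0.0397, against a stated 0.044. The difference is conservative and unrelated to this point.
- 42/0.90 = 46.7, rounded up to the 47 to be dosed.

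**4. Effect on the reported rate.** The documents do not give the number of such subjects. Assume t = 1 to 3, all non-responders, with 16 responders observed. Limits are exact 95% (Clopper–Pearson).

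| Omitted | Rate | 95% interval |
|---|---|---|
| 0 | 16/42 = 38.1% | 23.6–54.4% |
| 1 | 16/41 = 39.0% | 24.2–55.5% |
| 2 | 16/40 = 40.0% | 24.9–56.7% |
| 3 | 16/39 = 41.0% | 25.6–57.9% |

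**5. Effect on pass/fail when the true rate over all subjects is 25%.** Two cases, with the cut-offs unchanged:
- (a) The set shrinks to 42 − t. The rate among the rest is 0.25/(1 − t/42) = 0.2561, 0.2625, 0.2692. Pass probability: 0.0394, 0.0391, 0.0386.
- (b) 42 evaluable subjects remain out of 47 dosed. The rate is 0.25/(1 − t/47) = 0.2554, 0.2611, 0.2670. Pass probability: 0.0475, 0.0568, 0.0679.

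Against the baseline of 0.0397, case (a) is marginally lower and case (b) higher.

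**The case against.** The strongest reply is that 5.2 contains a slip of wording that the rest of the protocol resolves. Its heading is about stopping drug, 5.6 sends 5.2 toxicities to drug discontinuation by cross-reference, and 5.4 schedules the month-6 evaluation. Section 5.6 ends research visits, apart from the safety visit, only for GVHD progression or relapse, not for toxicity. On intent this stands. It does not change what the two sentences tell a site to do.

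On the analysis set, 10.1 excludes only dropouts unrelated to treatment, which implies that toxicity stops stay in. That also stands, and it makes the gap narrower. But the implication conflicts with the inclusion rule and gives no response status. Some of these subjects would be failures by another route: 5.1 encourages steroid cover after an abrupt stop, and 5.1.1 treats prednisone above the enrollment dose as failure. Since steroid cover is optional and may stay at or below that dose, not everyone is caught.

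A reader might infer that literal removal would also cut off safety follow-up, because it could occur 14 or 28 days after the last dose, before the safety visit. The documents do not support this. Section 9.0 says "All subjects will be closely followed for toxicity from the time of informed consent until 30 days after last administration of study medication" and requires serious events to be followed to resolution. Sections 5.2 and 5.5.6 require retesting within 2–7 days for grade 3–4 toxicity. None of these exempts the 5.2 subgroups.

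**Conclusion.** The concern holds as a minor inconsistency with a real, narrow gap behind it. Section 5.2 uses the protocol's term for study withdrawal where the surrounding text indicates drug cessation with continued evaluation. Section 10.1 does not state how a drug-toxicity stop without a month-6 assessment is counted.

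Leaving such subjects out would bias the reported response rate upward by about 1 percentage point per omitted non-responder at 16 responders. This assumes that those omitted would not have responded. The range of 1 to 3 subjects is also an assumption, and the true number may be nil.

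Two stronger conclusions are tempting but not supported. The first is that the trial's error rate is inflated: that holds only if 42 evaluable subjects remain after the omissions, and if the set shrinks the pass probability barely moves. The second is that the lower confidence limit passing 25% at three omissions would change the outcome: the decision rule is a count of 16 or more responders, so the limit decides nothing. Nor does the plan state an intention to exclude toxicity stops; it is silent on their status.

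**What to change.** In both 5.2 sentences, replace the removal wording so that these subjects permanently discontinue ruxolitinib and remain in the study for the month-6 GVHD evaluation in 5.4.

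In 10.1, add: *Subjects who stop ruxolitinib for toxicity before 6 months stay in the full analysis set. They count as non-responders if they have no GVHD evaluation within 14 days of month 6.* This covers all toxicity stops, not only the two 5.2 subgroups, so that every toxicity stop is counted by one rule.

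The stopping reasons in 5.6 and its limit on data collection after true study withdrawal need no change. The cost is two reworded sentences, one addition to 10.1 and a note to sites. No visit is added, because 5.4 already plans the evaluation. The downside is a slightly lower reported response rate if such evaluations are missing.
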